### 7.9.2.5 Determination of Patients/Data for Analysis

All subjects for whom defibrillation testing is attempted with the investigational device will be included in the analysis.

## 7.9.3 Ancillary Objective #1

Characterize appropriate and inappropriate shocks.

### 7.9.3.1 Hypothesis

This trial is for the purposes of gathering preliminary data on the investigational product, and so there are no hypotheses for this objective.

### 7.9.3.2 Performance Requirements

Performance requirements are not pre-specified for this objective. The endpoint is defined as a shock delivered by the EV ICD. Spontaneous arrhythmic episodes resulting in a shock will be adjudicated to determine the underlying rhythm.

### 7.9.3.3 Rationale for Performance Criteria

This is an observational study, and this objective is intended to characterize device performance with regard to sensing ventricular arrhythmias and delivering shocks when the episode either does not self-terminate or is not terminated by ATP. There are no pre-specified performance criteria.

### 7.9.3.4 Analysis Methods

Results will be summarized in aggregate using descriptive statistics. All shocks delivered by the device for spontaneous arrhythmias will be partitioned by whether the treated rhythm was a VT/VF episode, and by the specific rhythm of the episode. Both the number of episodes and the number of subjects experiencing such episodes will be reported, as well as the energy delivered.

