5.1. Duration

Subjects indicated for single-chamber ICD therapy will be recruited and implanted with the Medtronic EV ICD system. The study is expected to enroll over a period of 5 months. Subjects will undergo assessments at Pre-Hospital Discharge, 2 Weeks, 4-6 Weeks and 3 Month Visits, with follow-up for the primary safety objective at 3 months. Subjects will subsequently be followed up at 6-Months post-implant and every 6 months thereafter until study closure. Study closure is expected to occur after the EV ICD system is market-released [REDACTED]. Each subject’s participation is expected to be approximately 4 years.

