8.7. Pre-Hospital Discharge

Perform the following tests of the EV ICD System at the pre-hospital discharge. Prior to the subject being discharged, VF Therapies are required to be programmed ON and pacing therapies, as appropriate, should be programmed ON.

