## 3. Introduction

Today, implantable cardioverter defibrillator (ICD) therapy is the treatment of choice for patients who are at risk for sudden cardiac death due to life-threatening ventricular arrhythmias. Traditional ICD systems with transvenous leads are considered standard of care for primary or secondary prevention of arrhythmic death. However, these systems have limitations. Short- and long-term complications arising from ICD systems with transvenous leads, such as infection, pneumothorax, venous thrombosis, lead dislodgement, lead malfunction, and lead perforation, have persisted for decades as impediments to ICD usage. As a result, there is demand for novel ICD systems that circumvent the potential disadvantages of transvenous ICD systems by preserving the heart and vasculature.

Medtronic has developed an extravascular ICD system which uses a substernal lead vs. a transvenous or a subcutaneous lead. The Extravascular (EV) ICD system will have the capability, similar to a transvenous

system, to deliver ATP, post-shock pacing, and backup asystole pacing from a single device, while avoiding leads in the heart or vasculature.

The purpose of the EV ICD Pilot study is to characterize the preliminary safety and efficacy of the EV ICD system: a complete extravascular ICD system with the lead implanted substernally. The use of a pilot study design allows characterization of the EV ICD system in a limited number of subjects before launching into a large-scale pivotal study.

This Statistical Analysis Plan has been designed to document, the EV ICD Pilot Study design and the planned analyses to be included in interim and final reports.

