### 7.4 Handling of Missing, Unused, and Spurious Data and Dropouts

All available data will be included in the data listings and tabulations. Imputation of values for missing data for primary and secondary efficacy analyses will not be performed. With regard to the safety primary objective, subjects who exit the study prior to experiencing a major system or procedure-related complication will be censored at the date of their exit (in the case of the subject being lost to

follow-up, the subject will be censored at the date of last contact with the subject) in the calculation of any Kaplan-Meier freedom from complication rates.

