## 7.8 Interim Analyses

Once all enrolled subjects have had the opportunity to undergo implant defibrillation testing, the data at implant will be assessed for submission to one or more regulatory agencies. It will accompany data acquired through the point at which all subjects have had the opportunity to be followed to a 3-month visit, the accumulated data will be summarized for possible external dissemination. Descriptive statistics will be used to summarize the data.

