### 7.9.1.4 Analysis Methods

Results will be summarized in aggregate using descriptive statistics. The 90-day freedom from major complication rate will be generated using the Kaplan-Meier method, and the total number of major complications experienced by subjects for whom an implant is attempted will be summarized.

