### 7.9.3.5 Determination of Patients/Data for Analysis

All subjects successfully implanted with an EV ICD having at least one device interrogation post-implant will be included in the analysis. At minimum, all episodes occurring by the date at which all implanted subjects have had the opportunity to be followed for 3 months post-implant will be included.

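### Shock counts run to an open-ended calendar cut with no follow-up time or 3-month estimate, so a percentage of subjects would be neither a risk nor a rate

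*SAP*

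**What the plan says.** SAP 7.9.3.4, repeated in Protocol 12.5.4, splits shocks by whether the treated rhythm was VT/VF and by the specific rhythm. It then specifies the summary: "Both the number of episodes and the number of subjects experiencing such episodes will be reported, as well as the energy delivered".

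SAP 7.9.3.5 and Protocol 12.5.5 define the subjects as those successfully implanted who have at least one later device interrogation. They define the data as "At minimum, all episodes occurring by the date at which all implanted subjects have had the opportunity to be followed for 3 months post-implant". This is a calendar date with no upper limit, and the same date applies to every subject whenever that subject was implanted.

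The plan handles time explicitly for the primary safety endpoint. SAP 7.9.1.4 says: "The 90-day freedom from major complication rate will be generated using the Kaplan-Meier method". SAP 7.4 gives the matching censoring rule: "With regard to the safety primary objective, subjects who exit the study prior to experiencing a major system or procedure-related complication will be censored". Neither document has a corresponding provision for shocks.

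On when a shock can occur, Protocol 8.6.7.8 requires VF therapies to be off from the end of the implant procedure until the pre-hospital discharge evaluation. Protocol 8.7 then says: "Prior to the subject being discharged, VF Therapies are required to be programmed ON".

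**The concern.** A shock is an event that accrues over time. If earlier implants contribute more months than later ones, a statement such as 1 of 35 subjects has no time attached to it. It cannot be read as a 3-month risk or as a rate, and it would change if the same subjects were summarised at a later cut, which the minimum wording allows.

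This matters because the figures may travel. SAP 7.8 plans a summary for possible external dissemination with data through "the point at which all subjects have had the opportunity to be followed to a 3-month visit", and SAP 3 says that the document covers "the planned analyses to be included in interim and final reports". Protocol 9.3 names potentially fewer inappropriate shocks as a possible benefit over subcutaneous systems, and Protocol 5.2 says that pilot data will guide programming in the pivotal study. Readers of either report will want to know over what period the shocks occurred.

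No test, decision rule or sample size depends on this objective.

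**Working it through.** The documents state no shock rate, precision target or sample-size calculation for this objective, so there is no figure to reproduce. The check is what follow-up the plan's own timeline implies.

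**Inputs**
- Subjects implanted: 20 to 35 (SAP 6, Protocol 12.2).
- Enrolment: "The study is expected to enroll over a period of 5 months" (Protocol 5.1).
- Earliest cut: last implant plus 3 months (SAP 7.9.3.5). The 3-month visit window runs from day 90 to day 120 (Protocol Table 7).
- Scheduled interrogations after month 3: month 6, then every 6 months (Protocol 8.9).
- Assumptions: implants spread evenly over the 5 months, no exits, 90 days taken as 3 months and 120 days as 4. Protocol 5.1 gives the period for enrolment, not for implants.

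**Follow-up at the cut.** With implant time t uniform on 0 to 5 months:
- Cut at month 8 (5 + 3): follow-up is 8 − t, range 3 to 8, ratio 8/3 = 2.7, mean 5.5. Total: 20 × 5.5 = 110 and 35 × 5.5 = 192.5 patient-months.
- Cut at month 9 (window closed, 5 + 4): range 4 to 9, ratio 9/4 = 2.25, mean 6.5. Total: 130 and 227.5.
- Protocol 8.6 strongly recommends implant within 30 days of enrolment. If that lag spreads implants evenly over 6 months, the range at the earliest cut is 3 to 9, mean 6.0. Total: 120 and 210.

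**Where follow-up ends.** Device episodes are known only to the last interrogation. At the month-8 cut, the share with at least 6 months is (8 − 6)/5 = 40%. If the last interrogation is the scheduled one at month 3 or 6, the mean is 0.6 × 3 + 0.4 × 6 = 4.2 months. The totals are 20 × 4.2 = 84 and 35 × 4.2 = 147, which is 1 − 4.2/5.5 = 24% lower. Unscheduled interrogations would narrow the gap. The end point therefore has to be stated.

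**What a crude percentage would show.** Let r be the true 3-month risk (assumed, since the documents give none), with a constant hazard h = −ln(1 − r)/3 and shocks known up to the cut. For follow-up uniform on a to b months, the expected crude proportion is 1 − [exp(−ah) − exp(−bh)] / [(b − a)h].

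| Cut | Follow-up (months) | r = 5% | r = 10% | r = 15% |
|---|---|---|---|---|
| Earliest | 3 to 8 | 8.9% | 17.5% | 25.5% |
| Day 120 | 4 to 9 | 10.5% | 20.3% | 29.5% |
| A later cut, for illustration | 12 to 17 | 21.9% | 39.8% | 54.3% |

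If shocks are known only to the scheduled month-3 or month-6 interrogation, r = 10% gives 0.6 × 10% + 0.4 × (1 − 0.9²) = 6% + 7.6% = 13.6% at the earliest cut. These figures show the mechanism and are not predictions.

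**Precision of a 3-month estimate.** Every subject can reach 3 months at the earliest cut, so exact (Clopper-Pearson) 95% limits indicate what to expect. With no events the upper limit is 1 − 0.025^(1/n): 16.8% for n = 20 and 10.0% for n = 35. One subject of 35 is 2.9% (0.1% to 14.9%).

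**The case against.** The strongest reply is that SAP 7.9.3.3 describes this objective as characterising how the device senses ventricular arrhythmias and delivers shocks. On that reading the question is about episodes: when the device shocked, what was the rhythm? Counts by rhythm answer it. The SAP never calls the subject count a risk, a rate or a 3-month figure, there is no hypothesis, and descriptive statistics do not preclude reporting follow-up. This stands as a reason to treat the point as minor. It does not supply a time base for the number of subjects, which the plan also reports.

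The plan does give some context: all available data are listed (SAP 7.4), a flow diagram shows follow-up stages with missed visits, deaths and exits (SAP 7.1.1), and follow-up compliance is summarised (SAP 8). None of these is a patient-month denominator or is linked to shocks.

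Two stronger readings are tempting and are not supported. One is that shocks are reported as bare counts only; the rhythm split and the energy delivered are also planned. The other is that confining the analysis to spontaneous arrhythmias would lose inappropriate shocks, such as those caused by oversensing. The word most naturally means not induced, the split has a class for rhythms other than VT/VF, and Protocol 11.2 already bases inappropriate therapy on the adjudicated rhythm and the device episode log. No loss of shocks is shown.

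**Conclusion.** The point holds as a minor one, and acting on it is a cheap improvement. As planned, the shock summary has no follow-up time, no fixed time point and no censoring rule, and its cut is open-ended. The subject count divided by N would mix follow-up that differs by up to 2.7-fold at the earliest cut, and the result would shift with the cut chosen.

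The 3-to-8-month range rests on even implants over 5 months and no exits. The size of the gap between a crude percentage and a 3-month risk also needs an assumed risk and a constant hazard, so it should not be quoted as an expected bias. The absence of a time base does not depend on any of these assumptions.

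**What to change.** In SAP 7.9.3.4 and Protocol 12.5.4:

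1. Report total patient-months beside the episode and subject counts, measured from implant to the last device interrogation before exit, explant or the data cut.
2. Report, separately for appropriate and inappropriate shocks, the Kaplan-Meier proportion of subjects with a first shock by 90 days post-implant. Use the same origin, censor at the same end point, and give a 95% confidence interval. If there are no events, give the exact binomial upper limit.
3. State that VF therapies are off between the end of the implant procedure and pre-hospital discharge (Protocol 8.6.7.8 and 8.7), so that this short period carries no shock risk although it is counted.

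The cost is small. Save-to-media files are already collected at implant and at every later scheduled visit (Protocol Table 4), and Kaplan-Meier is already used for the safety endpoint. Under Protocol 12.1, a change of analysis method needs an amendment only if it alters a principal feature; otherwise the change and its justification go in the study report. The downsides are a little extra analysis and the wide intervals that 20 to 35 subjects allow. No procedure, sample size or primary analysis changes.

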### 7.9.3.5 Determination of Patients/Data for Analysis

All subjects successfully implanted with an EV ICD having at least one device interrogation post-implant will be included in the analysis. At minimum, all episodes occurring by the date at which all implanted subjects have had the opportunity to be followed for 3 months post-implant will be included.

## 7.9.4 Ancillary Objective #2

Characterize electrical performance (pacing capture thresholds, pacing impedance, sensing amplitudes) in a variety of postures and respiration cycles over time.

### 7.9.4.1 Hypothesis

This trial is for the purposes of gathering preliminary data on the investigational product, and so there are no hypotheses for this objective.

### 7.9.4.2 Performance Requirements

Performance requirements are not pre-specified for this objective. The endpoints are defined as pacing capture threshold, pacing impedance, and sensing amplitude. The pacing testing will be performed at pre-hospital discharge, as well as visits at 2 weeks, 4-6 weeks, and 3 months post-implant.

### 7.9.4.3 Rationale for Performance Criteria

This is an observational study, and this objective is for the purpose of characterizing device performance with regard to achieving pacing capture and determining sensing performance over time and at different postures. There are no pre-specified performance criteria.

### 7.9.4.4 Analysis Methods

Results will be summarized in aggregate using descriptive statistics. Pacing testing will be done at the postures provided in section 8.8.4.1. For each posture, and each follow-up visit, the proportion of subjects undergoing pacing testing will be reported, as well as the proportion for whom capture is obtained.

### 7.9.4.5 Determination of Patients/Data for Analysis

All subjects successfully implanted with an EV ICD having pacing tests for at least one posture will be included in the analysis.

## 7.9.5 Ancillary Objective #3

Characterize extracardiac pacing sensation.

### 7.9.5.1 Hypothesis

This trial is for the purposes of gathering preliminary data on the investigational product, and so there are no hypotheses for this objective.

### 7.9.5.2 Performance Requirements

Performance requirements are not pre-specified for this objective. The endpoint with regard to extracardiac pacing will be defined as:

- the presence of extracardiac muscle stimulation during pacing at implant as determined by the clinician
- the degree of pacing sensation as determined by the subject at follow-up testing

### 7.9.5.3 Rationale for Performance Criteria

This is an observational study, and this objective is characterizing extracardiac muscle stimulation and patient experience with pacing. There are no pre-specified performance criteria.

### 7.9.5.4 Analysis Methods

Results will be summarized in aggregate using descriptive statistics. Clinicians will be asked to assess presence of extracardiac muscle stimulation at implant, and subjects will be asked during follow-ups the degree of experienced extracardiac muscle stimulation for each pacing vector collected. Descriptive statistics will be used to summarize distribution among the subjects who underwent pacing. This objective will be analyzed using data from the implant, pre-hospital discharge, 2-week visit, 4-6 week visit, and 3 month visit.

### 7.9.5.5 Determination of Patients/Data for Analysis

All subjects successfully implanted with an EV ICD undergoing pacing testing or reporting symptoms attributed to being paced will be included in the analysis.

## 7.9.6 Ancillary Objective #4

Characterize asystole pacing.

### 7.9.6.1 Hypothesis

This trial is for the purposes of gathering preliminary data on the investigational product, and so there are no hypotheses for this objective.

### 7.9.6.2 Performance Requirements

Performance requirements are not pre-specified for this objective. The endpoint is whether the subject received pacing for asystole.

### 7.9.6.3 Rationale for Performance Criteria

This is an observational study, and this objective is for the purpose of characterizing prevalence of need for asystole pacing in this population. There are no pre-specified performance criteria.

### 7.9.6.4 Analysis Methods

Subjects receiving asystole pacing will be listed individually, with the amount of such pacing that each subject received.

### 7.9.6.5 Determination of Patients/Data for Analysis

All subjects successfully implanted with an EV ICD with at least one device interrogation post-implant will be eligible for the analysis. At minimum, all instances occurring on or before the date at which all implanted subjects have had the opportunity to be followed for 3 months post-implant will be included.

## 7.9.7 Ancillary Objective #5

Characterize lead position over time.

## 7.9.7.1 Hypothesis

This trial is for the purposes of gathering preliminary data on the investigational product, and so there are no hypotheses for this objective.

## 7.9.7.2 Performance Requirements

Performance requirements are not pre-specified for this objective. The endpoint is whether a subject's lead changed position over time (from implant to 3 months), and degree that it changed.

## 7.9.7.3 Rationale for Performance Criteria

This is an observational study, and this objective is for the purpose of characterizing degree of change in the EV ICD lead position. There are no pre-specified performance criteria.

## 7.9.7.4 Analysis Methods

Imaging (radiographs) will be performed at pre-hospital discharge, as well as visits at 4-6 weeks and 3 months. Lead position will be assessed and degree of movement will be summarized for each subject.

## 7.9.7.5 Determination of Patients/Data for Analysis

All subjects successfully implanted with an EV ICD will be eligible for the analysis.

## 7.9.8 Ancillary Objective #6

Summarize ATP performance with spontaneous arrhythmias.

### 7.9.8.1 Hypothesis

This trial is for the purposes of gathering preliminary data on the investigational product, and so there are no hypotheses for this objective.

### 7.9.8.2 Performance Requirements

Performance requirements are not pre-specified for this objective. The endpoint is defined as whether ATP was delivered by the EV ICD for a spontaneous ventricular tachycardia. Spontaneous arrhythmias will be adjudicated to determine the underlying rhythm.

### 7.9.8.3 Rationale for Performance Criteria

This is an observational study, and this objective is for the purpose of characterizing device ATP performance with regard to terminating monomorphic and polymorphic ventricular arrhythmias. There are no pre-specified performance criteria.

### 7.9.8.4 Analysis Methods

Results will be summarized in aggregate using descriptive statistics. All monomorphic and polymorphic ventricular arrhythmias with EGM will be partitioned by whether the treated rhythm received ATP, whether it successfully terminated as a result, and by the specific rhythm of the episode (monomorphic vs. polymorphic VT). Both the number of episodes and the number of subjects experiencing such episodes will be reported.

## 7.9.8.5 Determination of Patients/Data for Analysis

All subjects successfully implanted with an EV ICD having at least one device interrogation post-implant will be included in the analysis. At minimum, all VT/VF episodes occurring on or prior to the date by which all implanted subjects have had the opportunity to be followed for 3 months post-implant will be included in the analysis.

## 7.9.9 Ancillary Objective #7

Summarize adverse events.

### 7.9.9.1 Hypothesis

This trial is for the purposes of gathering preliminary data on the investigational product, and so there are no hypotheses for this objective.

### 7.9.9.2 Performance Requirements

Performance requirements are not pre-specified for this objective. The endpoint is an adverse event (see Table 11 in the CIP for definition of adverse event) experienced by a subject post-enrollment and prior to exit. All adverse events will be adjudicated by a Clinical Events Committee for relatedness to the EV ICD system and procedure.

### 7.9.9.3 Rationale for Performance Criteria

This is an observational study, and this objective is for the purpose of gathering data pertaining to device safety over at least the first three months post-implant. There are no pre-specified performance criteria.

### 7.9.9.4 Analysis Methods

Results will be summarized in aggregate using descriptive statistics. Counts and percentages of subjects experiencing system and/or procedure-related adverse events will be reported, as well as, in the case of system-related events, the specific component of the system to which the event was related.

### 7.9.9.5 Determination of Patients/Data for Analysis

All subjects for whom an implant of the investigational product is attempted will be included in the analysis. At minimum, all adverse events recorded by the date by which all implanted subjects have been followed at least 3 months post-implant will be included.

## 7.10 Safety Evaluation

Ancillary objective #7 is to summarize adverse events. See Section 7.9.9 for details.

## 7.11 Health Outcomes Analyses

A health outcomes analysis will not be performed beyond summarizing adverse events.

